### **Introductory Statement and Study Protocol**

#### **Introductory Statement**

The proposed study is a single-center proof-of-concept study, targeting a volunteer sample of adults with MDD who have failed an adequate trial of an SSRI or SNRI. After screening (week -1) and baseline (week 0) assessments and baseline neuroimaging, 60 subjects (with recruitment of up to 75 subjects, allowing for 20% attrition) will be randomly assigned in 1:1:1:1 ratio to treatment for 8 weeks with either double placebo, 5-HTP 100mg twice daily + Cr-matched placebo, Cr 5g daily + 5-HTP-matched placebo, or 5-HTP 100mg twice daily + Cr 5g daily. The treatment phase will again be followed by neuroimaging (week 8) as well as two post-treatment assessments (weeks 10 and 12).

#### Study Protocol

Table 1. Eligibility Criteria					
INCLUSION CRITERIA	RATIONALE				
Adults age 25-40 years inclusive	Maximizing recruitment while minimizing effect of age-related degeneration on MRI findings				
Current diagnosis of MDD identified by the SCID-5	Confirmation of target clinical condition				
Current HAM-D 17 score of $\geq$ 16	Confirmation symptoms at least moderately severe				
Adequate adherence to any FDA approved SSRI or SNRI for at least 8 weeks	t Confirmation of treatment-resistance				
Right-handed	Facilitate brain coregistration				
Residing at $\geq$ 4000 ft for at least 12 weeks	Ensure homogeneity with respect to hypoxic exposure				
EXCLUSION CRITERIA	RATIONALE				
Any non-MDD and non-anxiety psychiatric diagnosis, as identified by the SCID-5	y Minimize diagnostic heterogeneity and risk of adverse eve				
History of or current diagnosis of renal disease, such as chronic renal failure, acute renal failure or end stage renal disease	Some reports that creatine worsens renal disease				
Current colitis or diverticulitis	Facilitate recognition of serotonin syndrome				
History of or current pulmonary disease	Facilitate recognition of EMS, minimize variation in hypoxi between subjects				
Current smoking	Minimize variation in hypoxia between subjects				
History of cardiac disease or QTc > 500ms	Minimize risk of sudden cardiac death				
History of fibromyalgia or any rheumatological condition	Facilitate recognition of EMS				
History of or current seizure disorder	Minimize risk of seizure				
Current serious suicide risk identified by the Columbia Severity	Minimize risk of suicide in the study				
Suicide Rating Scale	······································				
Current treatment with an antipsychotic, mood stabilizer, or non-SSRI or SNRI antidepressant except for bupropion at FDA-approved doses or trazodone up to 200mg, or use of any supplements apart from standard multivitamins	clinical homogeneity of group				
Positive pregnancy test, pregnancy, failure to use adequate birth control method	Risks for fetus of interventions not adequately characterized				
Previous diagnosis of serotonin syndrome or evidence of serotonin syndrome	Minimize risk of serotonin syndrome				
Pre-existing eosinophilia (absolute eosinophil count	Facilitate recognition of EMS				
Contraindications to MRI: ferromagnetic implants, implanted devices, claustrophobia	Maximize MRI safety				
STUDY WITHDRAWAL CRITERIA	RATIONALE				
Intolerable or clinically significant side effects to creatine or 5-HTP	Subject safety				
Hospitalization for suicidal ideation/suicide attempt	Subject safety				
Initiation of any excluded psychotropic medication (antipsychotic, mood stabilizer or antidepressant)	Minimize risk of adverse drug-drug interaction				
Discontinuation of or inadequate adherence to FDA-approved SSRI/SNRI	This is an augmentation study				
Initiation of any excluded serotonergic medications	Minimize risk of serotonin syndrome				
Evidence of serotonin syndrome	Subject safety				
Evidence of EMS	Subject safety				
	Research involving prisoners is generally prohibited				

Positive pregnancy test, pregnancy	Subject safety
a. Inclusion and Exclusion Criteria: Inclusion and	nd exclusion criteria are detailed in Table 1:

**b.** Study Withdrawal Criteria: A participant will be withdrawn from the study if he or she experiences intolerable or clinically significant side effects to the study intervention (including the development of serotonin syndrome or eosinophilia-myalgia syndrome), hospitalization for suicidal ideation or suicide attempt, develops a positive pregnancy test or gives other evidence of pregnancy, is incarcerated, initiates any excluded medication, or discontinues or changes the baseline antidepressant. In addition, the principal investigators retain the right to withdraw participants from the study without their permission, in the event they are unwilling or unable to maintain adherence to the research protocol.

c. Procedures: All procedures performed by study personnel are research-related. None of the study activities will be considered standard of care. There will be no cost to study subjects for their participation. Participants will be compensated for their time and travel. Table 2 outlines the schedule of study procedures for clinical participants. Study visits will be supervised by a boardcertified/board-eligible psychiatrist and will be conducted either by a board-certified/board-eligible psychiatrist or a bachelor's level research assistant with training in the specific measures used. Physical examinations and laboratory interpretation will be conducted by a board-certified/boardeligible psychiatrist. Consent will be obtained before any study procedures are initiated. Potential participants will be informed of the study and offered a consent form to review. They will be encouraged to discuss study participation with their relatives. If a potential participant expresses interest in study participation, the informed consent process will be conducted. After the informed consent process, individuals will be offered time to consider study participation and to ask questions. Subjects will have the opportunity to discuss the study with a study team member in a setting free of coercion. The language of the informed consent form is written at a level easily understood by the subject and any questions asked by the subject will be answered honestly and without bias. A specific meeting time will be set up between a study team member and the participant where the entire informed consent document will be carefully explained in its entirety. The length of the meeting will be designed so there is the necessary amount of time for all questions to be answered. Subjects will be separately consented for blood sample storage for later genetic testing and will be allowed to opt-out of this procedure while still participating in the other aspects of the study.

To determine if an individual is eligible for study participation, a screening visit will be conducted. Initially, a HAM-D17 will be administered to determine if the patient exhibits depressive symptoms that are sufficiently severe for inclusion in the study. The duration of the patient's current residence and the altitude of that residence will be assessed. Next, the SCID-5 will be administered to confirm a diagnosis of a current major depressive episode. In addition, subjects will be screened for other DSM-5 disorders using the SCID-5 to assess exclusion criteria. Afterward, the MADRS, C-SSRS, BAI, YMRS, ATRQ, and CGI-S will be administered. All participants will receive a pregnancy test unless they report a history of menopause or hysterectomy. Study subjects will receive a baseline BUN/creatinine (to assess for renal insufficiency), CBC (to screen for pre-existing eosinophilia), measurement of whole blood serotonin, vitals including pulse oximetry, and a baseline focused physical. Subjects will be asked to be fasting for at least 3 hours prior to the blood draw. The blood draw will occur between 2 and 5pm to minimize circadian variation in serotonin levels. Subjects will be given an internet link and passcode to complete the Diet History Questionnaire II (DHQ-II) and asked to do this at home.

An EKG will be performed to evaluate the QT interval and to screen for other evidence of cardiac disease. They will also be screened for evidence of serotonin syndrome using the Hunter Criteria. A complete medical and psychiatric history (focused on illness duration, length of current

treatment, treatment history, and history of medical illnesses that preclude participation, e.g., renal disease, pulmonary disease, rheumatologic disease, diabetes, gastrointestinal disease, pregnancy, seizure disorder, serotonin syndrome) will be completed.

After the screening visit, participants will have a **baseline** visit after one week with the MRI happening + 4 days from the baseline visit, prior to the start of treatment. At the baseline visit, the HAM-D17, MADRS, C-SSRS, BAI, YMRS, and CGI-S will be administered. Vital signs will be checked and a physical exam performed if patient symptoms indicate a need. Whole blood serotonin will be drawn. Subjects will be asked to be fasting for at least 3 hours prior to the blood draw. The blood draw will occur between 2 and 5pm to minimize circadian variation in serotonin levels. Participants will be evaluated for serotonin syndrome using the Hunter Criteria. Baseline P-MRS and resting state fcMRI will be completed. After initiation of treatment, **subjects will be** reevaluated at 1, 2, 4, 6, and 8 weeks (+3 days). At each these visits, the HAM-D17, MADRS, C-SSRS, BAI, YMRS, and CGI-S will be administered again. Subjects will be asked to be fasting for at least 3 hours prior to the blood draw. Whole blood serotonin will be drawn. The blood draw will occur between 2 and 5pm to minimize circadian variation in serotonin levels. Follow-up P-MRS and resting state fMRI will be completed at week 8. Vital signs with pulse oximetry, focused physical exam if indicated, collection of urine for pregnancy screening if indicated, recording of concomitant medications, self-reported drug use, medication compliance assessment, study medication dispensing, and screening for treatment-related adverse effects will also be undertaken. Screening for treatment-related adverse effects will include application of the Hunter Criteria for serotonin syndrome as well as evaluation for symptoms of eosinophilia-myalgia syndrome. If subjects exhibit symptoms of eosinophilia-myalgia syndrome, a CBC with automated differential will be obtained. Finally, participants will be seen for follow up visits at 2 weeks and 4 weeks (+3 days) after completion of 5-HTP/Cr supplementation. Measure at these visits will include the HAM-D17, MADRS, C-SSRS, BAI, YMRS, CGI, DESS, vitals with pulse oximetry if indicated, focused physical exam if indicated, and evaluation for serotonin syndrome and EMS. Again, if symptoms of EMS are present, a CBC with automated differential will be obtained. After the screening visit. Participants can request study visits by videoconference with the exception of briefly dropping by the clinic for a blood draw and/or MRI as indicated in the schedule below.

	Screening	Baseline	Treatment					Follow-up		
Week	-1	0	1	2	4	6	8	10	12	
SCID-I	Х									
HAM-D17	Х	Х	Х	Х	Х	Х	Х	Х	Х	
MADRS	Х	Х	Х	Х	Х	Х	Х	Х	Х	
C-SSRS	Х	Х	Х	Х	Х	Х	Х	Х	Х	
BAI	Х	Х	Х	Х	Х	Х	Х	Х	Х	
CGI-S	Х	Х	Х	Х	Х	Х	Х	Х	Х	
YMRS	Х	Х	Х	Х	Х	Х	Х	Х	Х	
DESS								Х	Х	
Medical History	Х									
Diet History Questionnaire II	Х									
ATRQ	Х									
Hunter criteria		Х	Х	Х	Х	Х	Х	Х	Х	
Screening for EMS			Х	Х	Х	Х	Х	Х	Х	
Side-effect screening			Х	Х	Х	Х	Х			
Pregnancy test**	Х	Х	Х	Х	Х	Х	Х			
BUN/Creatinine	Х									
CBC with differential	Х		Х*	X*	X*	X*	X*	X*	X*	
Whole-blood 5-HT (fasting for > 3 hours; drawn	Х	Х	Х	Х	Х	Х	Х			
between 2:00 and 5:00pm										
EKG	Х									
Vitals including pulse-oximetry	Х	Х	Х	Х	Х	Х	Х	Х	Х	
Focused physical exam	Х		Х*	X*	X*	X*	Χ*	X*	X*	
Review of current medications	Х	Х	Х	Х	Х	Х	Х			
 P-MRS		Х					Х			
Resting State fMRI		Х					Х			

Table 2. Study Procedures for Clinical Subjects

\* = only if clinically indicated by presence of adverse symptoms or symptoms suggestive of EMS or serotonin syndrome

\*\* = all female subjects, unless reporting menopause, hysterectomy, tubal ligation or currently using an intrauterine device (IUD)

Once entered into the study, participants will be 1:1:1:1 randomized to receive either Cr+ placebo, 5-HTP+placebo, 5-HTP+Cr, or placebo+placebo. Block randomization using a SAS code, PROC PLAN with Block, will be used to ensure equal treatment allocation within each block. The study will be conducted as a double-blind trial, with neither participants nor research staff aware of participant assignment. Except in cases of medical emergency, the double-blind will not be "broken" until recruitment is closed and the final participant has completed 8 weeks of treatment and 4 weeks of follow-up. We anticipate an attrition rate of ~20% based on our pilot study (where attrition was 13%), and so will plan to recruit a total of 75 subjects, for a total recruitment of 60 subjects. The blind will be broken following the culmination of the study or at the request of a medical professional dealing with a medical emergency in a case in which it would help a study participant.

**d. Study Drug Dosing:** Cr doses will be 5g by mouth daily. 5-HTP doses will be 100mg BID. These doses are based those most commonly used in clinical trials or in historical practice. However, with natural products it is often unclear what the optimal doses are to balance safety and efficacy. For Cr, a dose of 5g was selected because this was the dose used effectively by Lyoo *et al.* (2012) and in our pilot study of 5-HTP + Cr. A 5-HTP dose of 100mg twice daily was selected because this is equivalent to the average total daily dose of 200mg given as a treatment option for depressed patients . We have elected to provide patients with twice daily dosing because the half-life of 5-HTP is estimated to be  $4.3\pm2.8h$ . In previous studies, 200mg given as a single daily dose was well tolerated with few side effects reported.

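### Withdrawal rule targets serotonergic medications, but the entry exclusion has no such heading, so an asymptomatic person already taking another one can be randomised to 5-HTP

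*Combined protocol and SAP*

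**What the plan says.** Every participant must already be taking an SSRI or SNRI (Table 1, inclusion criteria). "Discontinuation of or inadequate adherence to FDA-approved SSRI/SNRI" leads to withdrawal, so that drug continues throughout.

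The entry exclusion on co-medication in Table 1 reads "Current treatment with an antipsychotic, mood stabilizer, or non-SSRI or SNRI antidepressant except for bupropion at FDA-approved doses or trazodone up to 200mg", and goes on "or use of any supplements apart from standard multivitamins". A separate exclusion covers "Previous diagnosis of serotonin syndrome or evidence of serotonin syndrome". Anxiety disorders are allowed, because the psychiatric exclusion is "Any non-MDD and non-anxiety psychiatric diagnosis, as identified by the SCID-5".

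Among the withdrawal criteria in Table 1 is "Initiation of any excluded serotonergic medications", with limiting serotonin syndrome as its rationale. A separate row covers newly started psychotropics and lists its three classes in parentheses. Paragraph b (Study Withdrawal Criteria) withdraws anyone who "initiates any excluded medication" and gives no further list.

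Paragraph f (Potential Risks) states that 5-HTP raises the risk of serotonin syndrome. Paragraph j (Screening for Serotonin Syndrome) identifies the combination of several serotonergic drugs as the hazard and describes monitoring for it. Neither paragraph restricts co-medication.

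**The concern.** The plan treats starting an excluded serotonergic drug during the study as reason enough to stop. One would expect the entry criteria to bar people already taking such drugs, since the exposure alongside 5-HTP is the same whether the other drug began before randomisation or after it. The entry row is instead organised by psychiatric drug class plus supplements. What can be read of its rationale concerns the homogeneity of the group, not serotonin syndrome.

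At stake is participant safety in the two arms that contain 5-HTP. No sample size, power or error rate depends on this point.

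**Working it through.** No formula applies. The check sets the rules side by side and follows one kind of participant through them.

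**1. What the withdrawal row refers to.** The row has no list of its own. There are two ways to read it.

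- *Narrow reading.* The word *excluded* points back to the entry exclusions, as it does in the psychotropic row and in paragraph b. The row then covers the serotonergic members of the four entry headings, and entry and withdrawal rules agree for those drugs. This is the natural reading.
- *Wide reading.* A broader list was intended. That list does not appear in the available text and is not applied at entry. Starting such a drug would then force withdrawal, while already taking it would not prevent randomisation.

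**2. A serotonergic drug outside the four headings, on the narrow reading.**

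| Rule | Does it stop an asymptomatic person? |
|---|---|
| Entry exclusion on co-medication (Table 1) | No: none of the four headings applies |
| Entry exclusion for serotonin syndrome (Table 1) | No: needs a past diagnosis or present evidence |
| Hunter Criteria at screening and baseline (paragraph c) | No: detects signs, not exposure |
| Medication review at weeks -1 and 0 (Table 2) | No: the drug is recorded, but matches no heading |
| Withdrawal rows in Table 1 and paragraph b | Not clearly: the drug is not an excluded one |

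Table 2 as extracted marks the Hunter Criteria from baseline onward, while the text of paragraph c also places them at screening. The result is the same either way.

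**3. Is there a route in?** Anxiety diagnoses are permitted. A drug taken for anxiety that is not an antidepressant, antipsychotic, mood stabilizer or supplement falls under no heading. The documents do not say whether any such drug is serotonergic. That is for the study clinicians to decide.

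**4. Exposure after randomisation.** Allocation is 1:1:1:1 and 5-HTP is in two arms (with placebo and with creatine), so the chance of receiving it is 2/4 = 1 in 2.

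**5. Where a rule could be applied.** Table 2 schedules a medication review at weeks -1, 0, 1, 2, 4, 6 and 8, which is 7 reviews: 2 before treatment and 5 after it starts.

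**6. Could the missing heading be an extraction loss?** Table 1 shows three visible faults: the rationale of the co-medication row begins mid-phrase, the eosinophil threshold is cut off, and the row on prisoners has lost its criterion (paragraph b supplies incarceration). None of these suggests a lost serotonergic entry row, and the co-medication criterion itself reads as complete. Paragraphs b, c and j supply no such exclusion either. A lost row still cannot be ruled out.

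**The case against.** The strongest reply has four parts.

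*The term has a meaning.* This stands. A reader might infer that the serotonergic row is wholly undefined, but the natural reading takes it back to the entry headings. Nor is the row idle on that reading: the psychotropic row does not mention supplements, and the serotonergic row can cover those. What remains is the gap for drugs outside the headings.

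*The combination is not new in kind.* This also stands. A reader might infer that the gap lets in a third serotonergic agent where the plan foresaw only two. The documents do not support that count: trazodone up to 200mg is expressly permitted alongside the SSRI or SNRI, so if trazodone is counted as serotonergic, the plan already allows a further agent. The point is that other serotonergic drugs are admitted without the plan having considered them.

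*No qualifying drug is named.* This is true and limits confidence. The documents do not establish that an eligible person would be taking one. They also contain nothing that would exclude such a person, including any general discretion for the investigator to refuse entry.

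*The risk is managed by monitoring.* In part. "Study visits will be supervised by a boardcertified/board-eligible psychiatrist", vital signs and symptom questions are scheduled, a physician is on call, participants receive an information sheet, and evidence of the syndrome leads to withdrawal. It would be wrong to infer that the hazard is uncontrolled, or that the medication review has nothing to apply: it has the four headings. But these measures respond to symptoms, or to drugs under those headings. They do not prevent the combination in someone who is well. Visits may also be conducted by a research assistant, who would be helped by an explicit rule.

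**Conclusion.** The concern holds in a limited form. The entry rule omits a hazard that the protocol itself names, and on the natural reading the withdrawal rule shares the omission. An asymptomatic person taking a serotonergic drug outside the four headings can be randomised, with a 1 in 2 chance of 5-HTP on top of the required SSRI or SNRI.

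The number of such people cannot be estimated, because no co-medication rate is given; it may be small. The conclusion rests on two assumptions: that some relevant serotonergic drug lies outside the four headings, and that the source Table 1 contains no row lost in extraction. Confidence is medium. The change is worth making because it is cheap and acts before dosing, whereas the present controls mostly act once symptoms appear.

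**What to change.** First check the source Table 1 for a lost row or cell. If there is none:

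1. Add an entry exclusion for current use of any serotonergic medication other than the baseline SSRI or SNRI and the already permitted bupropion (at approved doses) and trazodone (up to 200mg). The study clinicians should set the list.
2. Have the serotonergic withdrawal row in Table 1 and paragraph b refer to that same exclusion, so that starting and already taking a drug are treated alike.
3. Apply the list at the 7 scheduled medication reviews: as an entry check at weeks -1 and 0, and as a withdrawal check at weeks 1, 2, 4, 6 and 8.

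This needs amendment wording only, with no new visit or procedure. The downside is a few additional screen failures or withdrawals, number unknown. Any extra withdrawals would draw on the planned attrition allowance of 75 - 60 = 15 participants.

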0.920. In an open-label study in depressed adolescents. PCr levels following Cr administration increased by 6.2%+ 9.6%. In a dose-finding study of Cr compared to placebo, the effect size for differences in PCr levels between the group receiving 4 grams of Cr daily compared to placebo was 0.7. We hypothesize that supplementation with Cr with or without 5-HTP will increase frontal cortical PCr levels. P-MRS neuroimaging will be performed at baseline, and repeated after 8 weeks of treatment with Cr + placebo, 5-HTP + placebo, or 5-HTP + Cr. To address our first hypothesis, a population-averaged generalized estimating equation (GEE) regression model is used for group comparison of the  $\Delta PCr$  (PCrWEEK 8 - PCrBASELINE) associated with Cr + placebo, 5-HTP + placebo, or 5-HTP + Cr. We will control for age, gender, and tissue partial volume effects (i.e., gray matter, white matter and cerebrospinal fluid) for in vivo phosphorus metabolite measurements made at two time points. The GEE for each subject, i has the form Yi(t)=Xi  $\beta$  +  $\epsilon_i$ , where Yi and Xi represent measured metabolite (PCr or  $\beta$ -NTP) levels and design matrix of covariates, respectively. The error term follows a multivariate normal distribution:  $\varepsilon_i \sim N(0, V_i)$ , where Vi is the variance of metabolite levels. We assume that measures taken closer to each other in time are more highly correlated than those taken further apart. Therefore, the first-order autoregressive structure, AR(1) is assumed such as  $cov[\varepsilon_i(t), \varepsilon_j(t')] = \rho^{|t-1|}$ tVi to model the dependence of the correlation on repeated measures from the same participant, where t is time variable and p is the correlation coefficient between the clinical symptom measures of two successive assessments. Assuming  $\rho = 0.30$ , expected MDES = 5% across the groups, and harmonic mean SD = 10%, respectively, a sample size of 60 participants (15 per group; 4 aroups) and 2 neuroimaging time points per participant has >80% power using the AR (1) GEE model at the 0.05 alpha level. In our open-label study, we experienced ~20% participant attrition. Imputation of missing data cannot be utilized for neuroimaging data. Therefore, anticipating a 20% attrition rate, we propose a target enrollment of 75 participants for the R61 phase.

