## e. Measures

We plan to use the following instruments for data collection:

- Structured Clinical Interview for DSM-5 (SCID-5)
- Hamilton Depression Rating Scale (HAM-D)
- Montgomery-Asberg Depression Rating Scale (MADRS)
- Columbia Suicide Severity Rating Scale (C-SSRS)
- Clinical Global Impressions Scale (CGI) severity of illness subscale (CGI-S)
- Beck Anxiety Inventory (BAI
- Young Mania Rating Scale (YMRS)
- Discontinuation-Emergent Signs and Symptoms checklist (DESS)
- Serotonin Syndrome Screening-Hunter Criteria
- Eosinophilia-Myalgia Syndrome Screening
- Eosinophilia-Myalgia Participant Information Sheet
- Serotonin Syndrome Participant Information Sheet
- National Cancer Institute Diet History Questionnaire Version II (DHQ-II)
- Antidepressant Treatment Response Questionnaire (ATRQ)

**f. Potential Risks:** During the screening visit, participants may become emotionally upset when asked about their psychiatric history including suicide attempts, or physical and sexual abuse.

Participants may also experience discomfort when providing urine for pregnancy tests. It is possible that a participant's illness could worsen during the study. This could be related or unrelated to the study. If the participant's illness worsens to the point that they are a danger to herself or others, they will be referred for appropriate care. If the participant is hospitalized for worsening illness, they will be withdrawn from the study. Participants may experience gastrointestinal discomfort as a result of taking creatine or 5-HTP. Participants will be encouraged to take both medications with food to minimize this risk. Finally, as detailed above, supplementation with 5-HTP increases the risks of eosinophilia-myalgia syndrome and serotonin syndrome. Notably, in our pilot study, there were no serious adverse events attributable to the study drugs. Participants will be counseled about these risks, informed of the signs and symptoms of these conditions, provided with information sheets detailing the symptoms of these disorders in lay terms and describing steps to take for further evaluation if indicated, and will be screened for both conditions at each visit after the initiation of treatment.

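### The imaging change comparisons rest on completers: withdrawal ends follow-up as well as study drug, missing scans are not imputed, and no check for informative loss is planned

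*Combined protocol and SAP*

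**What the plan says.** **Who leaves.** Study Protocol, section b: "A participant will be withdrawn from the study if he or she experiences intolerable or clinically significant side effects to the study intervention". The sentence goes on to list "hospitalization for suicidal ideation or suicide attempt, develops a positive pregnancy test or gives other evidence of pregnancy", then incarceration, then anyone who "initiates any excluded medication, or discontinues or changes the baseline antidepressant". Investigators may also withdraw people who do not adhere to the protocol. Section f (Potential Risks) adds: "If the participant is hospitalized for worsening illness, they will be withdrawn from the study". In each case the participant leaves the study. The document does not separate stopping study drug from stopping follow-up, and it schedules no rating or scan after withdrawal.

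**What happens to the missing data.** Statistical Design and Power, item 1: "Imputation of missing data cannot be utilized for neuroimaging data". Attrition is handled by enrolment: "anticipating a 20% attrition rate, we propose a target enrollment of 75 participants for the R61 phase". The imaging endpoint is week 8 minus baseline, adjusted for age, gender and tissue partial volume (item 2 adds education level). No analysis population, intention-to-treat rule or missing-data sensitivity analysis is stated.

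**Two triggers are worded differently in different places.** For the antidepressant, Table 1 has "Discontinuation of or inadequate adherence to FDA-approved SSRI/SNRI", while section b has "discontinues or changes the baseline antidepressant". For hospitalisation, section b is limited to suicidality, while section f refers to worsening illness generally.

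**The concern.** Most of these triggers arise after randomisation and can depend on the assigned arm or on how the participant is doing. Side effects depend on the product: section f names gastrointestinal effects for both products, and serotonin syndrome and eosinophilia-myalgia syndrome for 5-HTP. Hospitalisation and antidepressant changes are linked to the course of the depression.

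If such participants have no week-8 scan and nothing is imputed, the change comparison is unbiased only if loss is unrelated to the outcome given age, sex, education and tissue composition. None of those covariates records why someone left. Enrolling more people restores precision but does not remove this bias. PCr:tP is the stated main determinant of sample size, so the comparison at risk is the one the trial was sized for.

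**Working it through.** **1. The plan's own figure.** Inputs from item 1: 60 evaluable (15 in each of 4 groups) and 20% attrition.
- Enrolment: 60 / (1 − 0.20) = 75, which reproduces the plan.
- Expected loss: 75 × 0.20 = 15.
- At the 13% pilot attrition quoted in section c: 75 × 0.13 = 9.75, about 10.
- If 60 are randomised, as the Introductory Statement can be read, and 20% then leave: 12 lost, 48 remain.

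**2. Which analyses depend on completing.**
- *PCr change:* needs both scans. Item 1 also writes the GEE in terms of metabolite levels, so a baseline-only participant could stay in the model but would add almost nothing about change.
- *Connectivity before and after treatment:* also needs both scans in practice.
- *Whole-blood serotonin:* drawn at baseline and weeks 1, 2, 4, 6 and 8, and analysed by linear mixed model (item 4). That model can use values observed before a participant leaves, although the before-and-after wording leaves unclear which visits enter.
- *HAM-D and MADRS:* rated at every visit, but the document describes no analysis of them.

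**3. Size of a possible bias in PCr change (assumed pattern).** Suppose that on one side of a contrast the 20% who leave are the worst on some measure, while loss on the other side is random.
- Shift in the completers' mean on that measure: φ(−0.84) / 0.80 = 0.28 / 0.80 = 0.35 SD.
- Shift in an outcome correlated r with it: 0.35 × 0.3 = 0.105 SD, to 0.35 × 0.5 = 0.175 SD.
- If item 1's SD of 10% is the SD of change: 0.105 × 10 = 1.05 points, to 0.175 × 10 = 1.75 points.
- If it is the SD of a level with ρ = 0.30, the change SD is 10 × √(2 × (1 − 0.30)) = 11.83: 0.105 × 11.83 = 1.24 points, to 0.175 × 11.83 = 2.07 points.

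Item 1's target difference is 5%.

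**4. Type I error under the same pattern.** Take 30 analysed per side (two arms pooled).
- Standard error in SD units: √(2/30) = 0.258.
- r = 0.3: 0.105 / 0.258 = 0.41; Φ(−1.96 + 0.41) + Φ(−1.96 − 0.41) ≈ 0.069.
- r = 0.5: 0.175 / 0.258 = 0.68; Φ(−1.96 + 0.68) + Φ(−1.96 − 0.68) ≈ 0.104.

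Simulation with 37 randomised and 30 analysed per side agrees, at about 7% and 10%. If only about half of that side's losses are outcome-driven, the error is roughly 5.5 to 7%. If selection is equal on both sides, the mean difference is zero and the error is about 5 to 6%.

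**The case against.** **Reach.** A reader might infer that every comparison is completers-only and that the depression scales suffer most. The documents do not support that. The bar on imputation covers neuroimaging alone, the serotonin model can use partial data, no analysis of the scales is specified to be biased, and no completer population is declared. For imaging it follows from the change endpoint.

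**The 15.** It is also tempting to say that the withdrawal rules cost 15 of 75 randomised participants. The 20% is attrition from all causes, and the document does not say how much comes from these rules. Nor is it settled that 75 are randomised: the Introductory Statement can be read as 60 randomised from up to 75 recruited, section c speaks of recruiting 75, and item 1 of enrolling 75. Some losses could precede randomisation, and those would bias nothing.

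**Selectivity.** The rules do not remove exactly those who do badly. Worsening without hospitalisation is not a trigger, the Table 1 adherence criterion concerns the SSRI or SNRI, withdrawal for protocol non-adherence is discretionary, and pregnancy and incarceration are largely unrelated to outcome. In a factorial design, 5-HTP-related withdrawals can also fall on both sides of the pooled creatine contrast, so purely one-sided selection is an extreme case.

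**Estimand.** For a proof-of-concept marker, PCr while on treatment is a defensible target. If leavers in the creatine arms gained nothing, a 5% effect in completers would be 0.80 × 5% = 4% in everyone. That is a different question, not an error.

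All four points narrow the concern. None supplies follow-up after withdrawal or a planned check on the imaging comparison.

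**Conclusion.** The point holds for the imaging change comparisons. The plan ends follow-up after events that plausibly depend on arm or outcome, says the missing scans cannot be imputed, and offers only a larger sample in response.

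A worst-case bias is about a fifth to two-fifths of the target difference (1.05 / 5 = 0.21 to 2.07 / 5 = 0.41). That rests on the one-sided pattern, the correlations and the reading of the SD, all of which are assumptions. The harm depends on loss differing between arms, and the documents cannot show whether it will.

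The blanket statement on imputation is stronger than it need be. What is analysed is a fitted metabolite value, not an image, and the baseline scan, repeated symptom ratings and compliance assessments are available as predictors. This is a worthwhile and cheap improvement, not a flaw that invalidates the trial.

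**What to change.** 1. Leave the rules for stopping study drug as they are. State that these events end study medication and not follow-up, and keep the already scheduled ratings and week-8 scan where consent, safety and regulation allow. Carve out cases such as incarceration, for which Table 1 itself cites the prohibition on prisoner research.
2. Analyse all available participants by assigned arm, and report the on-treatment completer analysis alongside it for the mechanistic question.
3. Replace the imputation sentence with a sensitivity analysis that multiply imputes the regional metabolite value from arm, baseline value, HAM-D and adherence.
4. State how many participants are to be randomised, and report losses by arm and reason, separating those before randomisation from those after.
5. Separately, reconcile the antidepressant trigger (Table 1 against section b) and the hospitalisation trigger (section b against section f), since who is removed depends on which is read.

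**Cost:** protocol wording, one sensitivity analysis and a disposition table; the visits and scans are already scheduled. The downside is that off-drug scans dilute the on-treatment contrast, which is why the completer analysis stays. Voluntary dropout will continue, so the sensitivity analysis is needed even if follow-up improves.
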